#### 11.1.3. Baseline Phase

Eligible subjects will be assessed at Baseline for their self-report of cigarette consumption, confirmed by a quantitative assessment of urine cotinine levels (nicotine metabolite). Urine cotinine levels will be measured from a urine sample and sent to a core laboratory for analysis.

The following nicotine craving and nicotine dependence/withdrawal questionnaires will also be administered at baseline, in order to measure the subjects' baseline levels. Subjects will be requested to refrain from smoking for two hours before the baseline visit and before all treatment/assessment visits.

- 1) Nicotine Craving Scale (7 point VAS scale)
- Self-administered Fagerstrom Test of Nicotine Dependence (FTND) (Heatherton et al., 1991)
- 3) Minnesota Nicotine Withdrawal Scale (MNWS) (Hughes and Hatsukam 1986).
- 4) Self-administered Tobacco Craving Questionnaire (TCQ-SF) (Troop et al., 2003).

Cognitive test questionnaires, including MMSE and BSRT, will be reported at baseline.

Baseline data are defined as the data generated during the baseline visit prior to the first DTMS/sham treatment. Subjects who have completed all assessments at the baseline visit will be randomized to either the DTMS treatment group or the sham control group. The baseline visit should be performed within 7 days of the screening visit.

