# 11.2.4. Fagerstrom Test of Nicotine Dependence (FTND) (Heatherton et al., 1991)

The Fagerstrom Test for Nicotine Dependence (FTND) assesses physical nicotine dependence. The earlier Fagerstrom Tolerance Questionnaire was improved by modification, and a revised scoring for the FTQ, called the Fagerstrom Test for Nicotine Dependence (FTND) was developed. The FTND consists of six of the original items (nicotine rating and inhalation have been eliminated) with revised scoring for two of the items (TTF - Time to the first cigarette of the day, and CPD - Cigarettes per day). The FTND has acceptable levels of internal consistency, and is closely related to biochemical indices of heaviness of smoking. The FTND scores will be assessed at Baseline, at the weekly visits during the treatment phase and at the 4 month follow-up visit.

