## 11.3.2. Nicotine Dependence (Craving and Withdrawal) Symptoms

Nicotine Dependence (Craving and Withdrawal) Symptoms will be measured by changes in the following scales:

- The Nicotine Craving Scale weekly means will be calculated and compared between treatment and sham groups.
- The Fagerstrom Test for Nicotine Dependence (FTND) composite score (sum of component scores) will be calculated and compared between treatment and sham groups.
- The Minnesota Nicotine Withdrawal Scale (MNWS) scores for the eight individual symptoms will be calculated and statistical comparisons will be performed for each individual symptom, comparing the treatment group to the sham group. Composite withdrawal symptom scores (sum of component scores) will also be calculated and compared.
- Tobacco Craving Questionnaire (TCQ- SF) composite tobacco craving scores (sum of component scores) will also be calculated and compared between treatment and sham groups.

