#### 13.9.5. Efficacy analyses

• The continuous quit rate (CQR) at the 6 weeks visit will be compared between the study arms with a chi-squared test. In addition the CQR will be modeled with logistic regression; baseline daily number of cigarettes smoked, sex and center will be used as covariates.

Prognostic factors and sensitivity analysis for the CQR at the 6 week and/or 4 month follow-up visits will be performed in the following manner: adjustment for other covariates such as demographics or other baseline characteristics (e.g., sex, age, race and history of smoking) may be performed by adding these variables to the above described logistic model.

- Weekly point prevalence abstinence rates will be analyzed in the same manner.
- Daily number of cigarettes smoked will be presented over time and analyzed with a repeated measures analysis of covariance model. Baseline daily number of cigarettes smoked, sex and center will be used as covariates.

The analysis will be presented for all subjects in the analysis set and for the non-quitters only.

 Effect on withdrawal symptoms as measured by weekly scales measuring nicotine craving and dependence/withdrawal, including Fagerstrom Test for Nicotine Dependence (FTND), Minnesota Nicotine Withdrawal Scale SelfReport (MNWS), Tobacco Craving Questionnaire–Short Form (TCQ-SF) and Nicotine Craving Scale.

Fagerstrom Test for Nicotine Dependence scores will be presented in tabular form and compared between the treatment arms with chi-squared tests.

Minnesota Nicotine Withdrawal Scale Self-Report scores, Factor structure of Tobacco Craving Questionnaire–Short Form scores, and Nicotine craving scale scores will be presented over time and analyzed with a repeated measures analysis of covariance model. Baseline daily number of cigarettes smoked, sex and center will be used as covariates.

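### Exploratory scale analyses leave out each scale's own baseline and test FTND scores by chi-squared, at a cost in precision and power only (low severity)

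*Protocol*

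**What the plan says.** Section 13.9.5 fixes two kinds of analysis for these scales.

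- **FTND:** "Fagerstrom Test for Nicotine Dependence scores will be presented in tabular form and compared between the treatment arms with chi-squared tests". No time point, score grouping or baseline term is given.
- **MNWS, TCQ-SF and craving:** the sentence that covers all three ends "Nicotine craving scale scores will be presented over time and analyzed with a repeated measures analysis of covariance model". The covariate list is the one that the section also uses for the quit rate and for daily cigarettes: "baseline daily number of cigarettes smoked, sex and center will be used as covariates". The scale's own baseline is not on it.

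Other sections bear on the choice:

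- Section 11.1.3 says that the craving and dependence/withdrawal "questionnaires will also be administered at baseline" and lists all four scales. Sections 11.2.3 to 11.2.6 repeat this scale by scale. For FTND: "The FTND scores will be assessed at Baseline, at the weekly visits during the treatment phase and at the 4 month follow-up visit".
- Section 11.3.2 says that the symptoms "will be measured by changes in the following scales", and that the FTND "composite score (sum of component scores) will be calculated and compared between treatment and sham groups".
- Section 11.2.4 describes the instrument: "The FTND consists of six of the original items". The total range is not given.
- Section 13.9.1 assigns the t-test or Wilcoxon test to continuous variables, and chi-squared or Fisher's exact test to proportions.
- Sections 13.2.3 and 13.9.2 make these endpoints exploratory, outside the testing hierarchy and mainly descriptive.

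**The concern.** Two pieces of information already in hand go unused.

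First, the baseline value of a craving or withdrawal scale is likely to be a better predictor of its later values than cigarettes per day. Leaving it out makes the treatment estimate less precise, and any chance difference between arms at baseline stays in that estimate. The covariate list does supply the outcome's own baseline where the outcome is daily cigarettes. The same list applied to the scales does not, which would fit wording carried over without adaptation, though that is an inference.

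Second, a Pearson chi-squared test on a table of scores ignores their order and spreads a shift in level over several degrees of freedom. It also ignores baseline. FTND is measured on the same schedule as the other scales and belongs to the same endpoint group, yet it alone gets an unordered test.

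At stake is a weak comparison on dependence and craving, which the device is hypothesized to affect (section 2.4). A non-significant FTND result could be taken as no effect on dependence when the test had little chance of finding one.

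**Working it through.** The protocol gives no SD, effect size or power for any of these scales, so it has no figure to reproduce. The check has three parts.

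**1. Sections side by side**

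| Question | Sections 11 and 13.9.1 | Section 13.9.5 |
|---|---|---|
| Baseline of each scale collected? | Yes, all four (11.1.3, 11.2.3 to 11.2.6) | Not in any scale's model or test |
| Measured as change? | Yes (11.3.2) | No change score or own-baseline term stated |
| FTND variable | Composite, a sum of components (11.3.2) | Scores in tabular form |
| Test for a continuous variable | t-test or Wilcoxon (13.9.1) | Chi-squared for FTND |

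**2. Gain from own-baseline adjustment**

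Let r be the correlation between a scale's baseline and its follow-up value (assumed). Adjustment leaves a fraction 1 − r² of the residual variance, so it removes r²:

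- r = 0.3: 0.3² = 0.09, or 9%
- r = 0.5: 0.5² = 0.25, or 25%
- r = 0.6: 0.6² = 0.36, or 36%

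These are upper figures. Whatever cigarettes per day, sex and center already explain comes off them.

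**3. Power of an unordered FTND test**

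Inputs: two-sided 5% level (section 13.9.2); a linear shift in score; k tabulated categories (assumed), giving k − 1 df when two arms are compared.

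Power = P[χ²(df, λ) > χ²(df, 0.95)], where λ is the noncentrality. A 1-df test has 80% power at λ = 7.85. With the same λ on more df:

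| Categories | df | 5% critical value | Power |
|---|---|---|---|
| trend or mean comparison | 1 | 3.84 | 80% |
| 3 | 2 | 5.99 | 71% |
| 5 | 4 | 9.49 | 60% |
| 11 | 10 | 18.31 | 43% |

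Holding λ fixed assumes that grouping the scores loses none of the shift. Any such loss would lower the 2-df and 4-df figures.

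**Simulation cross-check.** 3,000 trials per setting, with 82 per arm (the evaluable number in section 13.4). Assumed: integer scores from 0 to 10, SD 2.2, standardized difference 0.44, correlation 0.3, 0.5 or 0.7.

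| Analysis | Power |
|---|---|
| Chi-squared on the score table | 36–37% |
| Wilcoxon | 77–78% |
| t-test | 79% |
| ANCOVA on own baseline | 81%, 88%, 96% at r = 0.3, 0.5, 0.7 |

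At a standardized difference of 0.30 the figures are 15–18% for chi-squared, 46–48% for the t-test and 50%, 58% and 73% for ANCOVA. With no true difference, chi-squared rejected in about 4% of trials, so it holds its level.

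**The case against.** The strongest objection is that nothing decisive depends on these scales. They are exploratory and mainly descriptive, and neither the sample size nor the testing hierarchy involves them. For cigarettes per day, the repeated-measures endpoint that is in the hierarchy, the plan does adjust for the outcome's own baseline. This stands, and it sets the severity.

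It can also be said that the reference in section 11.3.2 to changes means that change from baseline is the response, or that baseline enters the repeated measures model as a response. Either is possible, but section 13.9.5 states neither, so the two sections need reconciling. Change scores would not make the adjustment redundant: in the simulation at a standardized difference of 0.44 they gave 63%, 76% and 93% power at r = 0.3, 0.5 and 0.7, below own-baseline ANCOVA each time.

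A third objection is that the FTND table might hold groups or items, not the total. Section 13.9.5 does not say, and no cut-points are given. This is why the power loss must be shown as a range. A plain chi-squared test on ordered groups would still ignore their order.

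Some stronger readings are tempting but lack support:

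- **The treatment estimates are biased.** Randomization protects against this. Chance imbalance adds noise.
- **The FTND test is invalid because of sparse cells.** Section 13.9.1 allows Fisher's exact test where appropriate.
- **The chi-squared test is repeated at every visit.** The plural in section 13.9.5 might refer to visits, items or categories, and no time point is named.

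**Conclusion.** The point holds at low severity. It concerns methods that the protocol fixes in writing, and for FTND the choice sits badly with the protocol's own general rule for continuous variables. The harm is confined to efficiency on exploratory endpoints.

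The size depends on two unknowns: the baseline-to-follow-up correlation and the number of FTND categories tabulated. Over the ranges shown, the lost precision runs from modest to about a third of the residual variance, before allowing for the existing covariates. The FTND power loss runs from about 9 points (80% to 71%) to about 37 points (80% to 43%). A reader should not infer that any primary or secondary conclusion is at risk.

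**What to change.** In section 13.9.5:

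1. Add the baseline value of the scale being analysed to the repeated measures models for MNWS, TCQ-SF and the Nicotine Craving Scale, keeping cigarettes per day, sex and center.
2. Replace the chi-squared tests for FTND by the same model applied to the composite with its own baseline, or by an ordinal or Wilcoxon method, and name the time point of the comparison. The tabulation can stay as a descriptive display.
3. Check that sections 11.3.2, 13.9.1 and 13.9.5 then agree on whether change is the response and on how FTND is scored.

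The cost is about two sentences, with no new data, visits or sample size. It should be done before unblinding, so that the choice cannot look driven by the data.

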### 13.9.6. Safety analyses

Adverse events (AE) will be presented by seriousness, severity and relation to treatment by treatment group. Serious adverse events will be listed and discussed individually. The incidence of potentially clinically significant vital sign measurements (BP, pulse and weight) will be presented at the 6 week and 4 month follow-up visits by treatment group. Descriptive statistics as well as changes from baseline will also be presented by study group at each scheduled visit.

Hearing loss will be presented in a tabular form at the 6 week visit by treatment arm. MMSE and BSRT will be tabulated at the 6 week and 4 month follow-up visits by treatment group.

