## 11.1.5. Follow up Phase

At the end of the 6-week period, participants who had quit smoking will be scheduled for a follow-up visit at 4 months (from the screening visit). Those who continue to smoke will complete an "end of study" form and will not be required to return for further followup. The 4 month follow-up visit will include the same assessments and questionnaires as the weekly visits. All attempts will be made to minimize drop-out and ensure that the study subjects present for the 4 month follow-up visit, including periodic study reminders.

All follow-up procedures are shown in the Time and Events Schedule (Attachment 1).

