# 13.2.4. Safety Endpoints

- The incidence, severity and frequency of all Adverse Events (AE), related and unrelated to the device treatment including seizures.
- Cognitive changes using the Mini Mental State Exam (MMSE) and the Buschke Selective Reminding Test (BSRT) cognitive tests.
- Vital signs and hearing loss measured by auditory threshold testing will be evaluated.

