### 13.8. Data Analysis Sets

13.8.1. Intent-to-Treat (ITT) Analysis Set

For safety analysis, the ITT analysis set (ITT-S) will consist of all subjects randomized. In accordance with the ITT principle, all subjects randomized who received at least one treatment (DTMS or Sham) will be kept in their originally assigned treatment group. For efficacy analyses, the ITT analysis set (ITT-E) will consist of all subjects who met all the inclusion/exclusion criteria and were randomized who received at least one treatment (DTMS or Sham) (defined as an average stimulation intensity of at least 110% of the motor threshold during treatment session no. 3 to the last treatment session) and have at least one post-baseline assessment available for analysis.

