### 15.2. Procedures

#### 15.2.1. All Adverse Events

All adverse events will be reported from the time a signed and dated informed consent form is obtained until completion of the last study-related procedure. Events meeting the definition of serious adverse events must be reported using the Serious Adverse Event Form, including serious adverse events spontaneously reported to the investigator within 30 days after the subject has completed the study (including post study follow up).

All events that meet the definition of a serious adverse event will be reported as serious adverse events, regardless of whether they are protocol-specific assessments. All adverse events, regardless of seriousness, severity, or presumed relationship to study treatment must be recorded using medical terminology in the source document and the CRF. Whenever possible, diagnoses should be given when signs and symptoms are due to a common etiology (e.g., cough, runny nose, sneezing, sore throat, and head congestion should be reported as "Upper respiratory infection"). Investigators must record in the CRF their opinion concerning the relationship of the adverse event to study treatment. All measures required for adverse event management must be recorded in the source document and reported according to sponsor instructions. In the case of a seizure, the investigators will provide to those patients experiencing a seizure a letter documenting that the seizure was experimentally produced. Other potential adverse events which could occur include psychiatric complications (e.g., mania, changes in behavior, hostility, agitation, depression and suicidality), headache, neck pain, intensification of existing headaches, tinnitus, and temporary or permanent hearing loss. The study personnel staff will be responsible for observing the study subjects during the weekly assessments and follow-up visits for such adverse events. In the case of an adverse event, the study investigator will prescribe the appropriate treatment and if appropriate, the subject will be terminated from the study to ensure subject safety.

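### Adverse events are observed for about 16 weeks in quitters and about 6 in continuing smokers, yet shown by arm with no common window, which can tilt the table against an effective device

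*Protocol*

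**What the plan says.** **Collection.** Protocol section 15.2.1 has all adverse events reported "from the time a signed and dated informed consent form is obtained until completion of the last study-related procedure". Footnote d of Appendix A says the same. Serious events reported spontaneously within 30 days after a subject completes the study are also included, whatever the smoking status.

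**Length of follow-up.** Under section 11.1.5, subjects who had quit by the end of the 6 weeks are booked for a visit at 4 months from screening. Those still smoking complete an end-of-study form and "will not be required to return for further followup".

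**Endpoint and presentation.** Section 13.2.4 defines the safety endpoint as "The incidence, severity and frequency of all Adverse Events (AE), related and unrelated to the device treatment including seizures". Section 13.8.1 sets the population: "For safety analysis, the ITT analysis set (ITT-S) will consist of all subjects randomized". Section 13.9.6 then says "Adverse events (AE) will be presented by seriousness, severity and relation to treatment by treatment group". The same section names visit times for vital signs, hearing, MMSE and BSRT, but none for adverse events.

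**Wording that does not fit section 11.1.5.** Section 11.2 speaks of all subjects being evaluated at each follow-up visit. Sections 11.2.7, 11.2.8, 11.4.1 and 11.4.4 place safety assessments at 4 months without limiting them to quitters.

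**The concern.** Read together, these sections make the time during which an adverse event can be recorded depend on the primary efficacy outcome. An arm with more quitters is watched for longer. Incidence and frequency of all events, including unrelated ones, grow with observation time, so the arm with more quitters collects more events even when the underlying risk is the same.

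At stake is how the safety table reads. If DTMS works, the table tilts against it; if it does not work, there is no tilt. The safety result therefore cannot be read separately from the efficacy result. This concerns the cumulative adverse event table. The primary efficacy test is not affected.

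**Working it through.** The protocol states no adverse event rate and no observation time, so there is no figure of its own to reproduce. The check builds the observation time from the protocol's inputs.

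**Inputs**
- Quit rates (section 13.4, sample size): sham 18%; a 20-point difference gives DTMS 38%.
- Quitters: 4 months from screening = 4 × 30.4375 / 7 = 17.4 weeks. Section 11.1.3 says "The baseline visit should be performed within 7 days of the screening visit", so this is 16.4 weeks from a baseline held 7 days after screening.
- Continuing smokers: 6 weeks.
- Drop-out: 37% (section 13.4). *Assumption:* drop-outs are observed for 3 weeks on average.
- *Assumption:* the share followed to month 4 equals the four-week quit rate. Section 11.1.5 does not define who counts as having quit.

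**1. Mean scheduled observation, no drop-out:** q × 16.4 + (1 − q) × 6
- DTMS: 0.38 × 16.4 + 0.62 × 6 = 9.95 weeks
- Sham: 0.18 × 16.4 + 0.82 × 6 = 7.87 weeks
- Ratio 9.95 / 7.87 = 1.26

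With equal quit rates the ratio is 1.00. With the pilot's three-week rates (44% and 13%) it is 10.58 / 7.35 = 1.44.

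**2. With 37% drop-out:** 0.37 × 3 + 0.63 × (result of step 1)
- DTMS: 1.11 + 0.63 × 9.95 = 7.38 weeks
- Sham: 1.11 + 0.63 × 7.87 = 6.07 weeks
- Ratio 1.22

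Here the quit rates apply to those who stay. If they are instead shares of all subjects, with drop-outs counted as non-quitters, and quitters are followed for 16 weeks, the times are 0.38 × 16 + 0.37 × 3 + 0.25 × 6 = 8.69 and 0.18 × 16 + 0.37 × 3 + 0.45 × 6 = 6.69 weeks, ratio 1.30.

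**3. Event-count ratio with no true difference.** Let f be the hazard after week 6 as a fraction of the on-treatment hazard, with 10 late weeks (16 − 6) and no drop-out:
ratio = (6 + 10 × f × 0.38) / (6 + 10 × f × 0.18)

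| f | Ratio |
|---|---|
| 0 | 1.00 |
| 0.10 | 6.38 / 6.18 = 1.03 |
| 0.25 | 6.95 / 6.45 = 1.08 |
| 0.50 | 7.90 / 6.90 = 1.14 |
| 1 | 9.80 / 7.80 = 1.26 |

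**4. Proportion with any event.** *Assumption:* 30% by week 6, exponential times, same hazard in both arms. For f = 1, a quitter's risk by week 16 is 1 − 0.7^(16/6) = 61.4%.
- DTMS: 0.62 × 30% + 0.38 × 61.4% = 41.9%
- Sham: 0.82 × 30% + 0.18 × 61.4% = 35.6%

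The gap of 6.3 points is wholly artefact. At f = 0.25 the figures are 33.7% and 31.7%, a gap of 1.9 points before rounding.

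**5. Serious events.** Adding 30 days (4.29 weeks) for everyone to the 16-week and 6-week windows: (9.80 + 4.29) / (7.80 + 4.29) = 14.09 / 12.09 = 1.17.

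**6. Common window.** Restricted to the scheduled first 6 weeks, the ratio is 6 / 6 = 1.00.

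**The case against.** **This belongs in the statistical analysis plan.** Section 13.9.6 fixes no denominator, no cumulative period and no test. A treatment-emergent window and person-time rates are ordinary analysis-plan content, and that plan is not at hand. It is true that a per-subject denominator is only inferred, from the word incidence in section 13.2.4 and the safety set in section 13.8.1. But the protocol itself fixes the outcome-dependent follow-up, and it commits to presenting all events by arm. An analysis plan could repair the combination, but the combination is set here.

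**A reader might infer that DTMS will show 22% to 26% more events.** The documents do not support that as a result. It needs an unchanged hazard after stimulation ends, attendance of every quitter at month 4, and equally intensive ascertainment. Section 11.4.5 assesses events at study visits, and Appendix A has 18 treatment visits in six weeks, then one visit about 10 weeks later. Section 13.4 itself reports high drop-out at the pilot's long-term time point. If, for illustration, 60% of quitters attend and the rest add nothing after week 6, the 1.22 falls to 1.14; with a 25% late hazard as well, it is 1.04.

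**A reader might also infer that the main safety comparison is biased throughout.** That is too strong. The presentation is descriptive, it separates events by relation to treatment, and serious events are discussed individually. Device-related events confined to the treatment weeks are unaffected. The 30-day extension also narrows the gap for serious events.

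**Section 11.2 says all subjects are evaluated at follow-up.** If that wording governed, and all attended month 4, the quit-dependent window would disappear. Section 11.1.5 is the specific rule and says otherwise. The conflict stands and has to be resolved.

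**Conclusion.** The point holds in limited form. Follow-up for adverse events depends on quit status, and the by-arm table has no common window. If DTMS has more quitters, the table tilts against it, mainly for late and unrelated events.

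At the planned quit rates, scheduled observation is 1.26 times as long on DTMS without drop-out and about 1.22 times with 37% drop-out; reading the quit rates as shares of all subjects gives 1.30. These ratios take section 11.1.5 as operative.

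The effect on event counts cannot be fixed from the protocol, which gives no adverse event rates. Under the stated assumptions it runs from 1.00 through about 1.08 to 1.22–1.26, the top being the case of an unchanged hazard with full month-4 attendance. The window ratio for serious events is about 1.17. The direction is certain only if quit rates differ and some events occur after week 6. Section 13.2.4 counts unrelated events and section 15.2.1 has staff watch for events at follow-up visits, so a late hazard of exactly zero is not what the protocol presumes.

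**What to change.** In section 13.9.6, make the main by-arm presentation of adverse and serious adverse events run from the first session to the week-6 visit, or to earlier termination, and report the weeks observed in each arm. Show events after week 6 separately, as rates per person-time among those actually followed. List events between consent and the first session apart.

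Reconcile section 11.1.5 with sections 11.2, 11.2.7, 11.2.8, 11.4.1 and 11.4.4 on who attends the 4-month visit, and define who counts as having quit for that purpose.

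The cost is wording and one table split. No new data are needed, assuming event onset dates are on the case report form. The downside is that late events leave the headline table, so the separate table must be reported beside it.
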